### **2.4 Rationale**

Etanercept has become a well-established agent in the management of RA. It can be used either as monotherapy or in combination with methotrexate to treat RA. Etanercept is commonly used in combination therapy after monotherapy with a first line agent such as methotrexate has failed. Patients report lower disease activity and improved quality of life with the incorporation of etanercept into their traditional DMARD therapies (Klareskog et al, 2004).

Recent studies including PRIZE (Emery et al, 2012), PRESERVE (Smolen et al, 2013), and DOSERA (van Vollenhoven et al, 2013a), have characterized the role of etanercept

on inducing and maintaining low disease activity in RA subjects. Importantly, these studies demonstrated that a significantly greater proportion of subjects taking combination etanercept plus methotrexate therapy are able to maintain low disease states compared to subjects taking methotrexate alone. The DOSERA study importantly demonstrated that most patients whose disease activity worsens after drug withdrawal are able to return to low disease activity ([van Vollenhoven et al, 2013b](#)).

Other studies provide insights regarding the role of etanercept as monotherapy in the maintenance of low disease states. In the COMET study ([Emery et al, 2010](#)) subjects who achieved DAS-28 remission on combination etanercept plus methotrexate were randomized to continue the combination therapy or to discontinue methotrexate and be treated with etanercept alone for one year. There was a numerically greater decrease in the percentage of subjects who maintained remission in the etanercept arm compared to the combination arm but the differences were relatively minor. In the CAMEO study, subjects with active RA were treated for 6 months with combination etanercept plus methotrexate ([Pope et al, 2013](#)). After 6 months the patients were randomized to continue on the combination or to be treated with etanercept monotherapy for the next 18 months. In patients who achieved low disease activity (DAS-28-ESR < 3.2) at month 6, the disease activity at 24 months was similar whether they discontinued methotrexate or remained on combination therapy. Combination treatment led to lower disease activity scores compared to etanercept monotherapy, however, in subjects with moderate to high disease activity at randomization (DAS-28-ESR > 3.2).

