### **3.1.1 Rescue Therapy**

After randomization, if a subject experiences disease worsening as defined below he/she will initiate rescue treatment with etanercept 50 mg once weekly (QW) plus methotrexate (10 to 25 mg). Those assigned to the etanercept plus methotrexate arm will continue on the assigned treatments. Subjects will receive methotrexate at the same dose that they were receiving at screening.

Original treatment assignments will remain blinded. Dispensing of etanercept plus methotrexate rescue therapy will be managed via the Interactive Voice and Web Response System (IXRS).

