## **10.5 Planned Methods of Analysis**

### **10.5.1 General Considerations**

Baseline demographics and disease characteristics will be summarized descriptively.

Summary descriptive statistics by each treatment group will be provided. For categorical endpoints, the descriptive statistics will contain the frequency and percentage. For continuous endpoints, the descriptive statistics will include the number of observations, mean, standard deviation, median, minimum, maximum and 95% confidence interval.

Non-responder imputation will be employed for the missing values of the primary endpoint. Secondary efficacy endpoints will be summarized using observed cases only. As supportive analysis, the primary endpoint will also be summarized using observed cases.

The statistical test for the primary efficacy endpoint will be two-sided with a significance level of 0.05.

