3.2 Sample Size

The sample size was determined from a hypothesis of superiority of etanercept monotherapy over methotrexate monotherapy. The proportion of subjects achieving SDAI remission after 52 weeks of double-blind treatment in the PRESERVE and COMET studies was used to estimate the treatment effects. PRESERVE was a two-period study conducted in subjects with RA who had moderate disease activity despite a stable dose of oral methotrexate for a minimum of 8 weeks at the time of screening. Among all subjects who were in SDAI remission at both week 28 and week 36 (the last two visits of the open-label run-in period), the proportion of subjects who were still in remission after the 52-week double-blind period was 86.1% and 38.1% for the etanercept plus methotrexate therapy and methotrexate monotherapy treatment groups, respectively. COMET was a two-period study conducted in subjects with active early RA. Among all subjects who received etanercept plus methotrexate therapy in Period 1 and were in SDAI remission at week 52, the last visit of Period 1, the proportion of subjects who were in still in remission after the 52-week double-blind Period 2 was 78.3% and 72.4%, respectively, for the etanercept plus methotrexate therapy and etanercept monotherapy treatment groups. Given key differences noted in this study, including the sustained period of remission prior to withdrawal, the response rate in the methotrexate monotherapy arm is approximated to be higher at 50%, with the response

rate in the etanercept monotherapy arm at approximately 72%. It is expected that compared to PRESERVE, subjects in the current study will have more stable disease at the time of randomization. Namely, subjects must be in very good disease control for 6 months prior to study entry and must be in SDAI remission at the end of a 24-week open-label run-in period.

The sample size is based on the adequacy to evaluate the efficacy of etanercept monotherapy compared to methotrexate monotherapy as measured by the primary endpoint of SDAI remission at week 48 at a significance level of 0.05. The sample size was also ensured to be sufficient to evaluate the efficacy of the etanercept plus methotrexate treatment arm compared to methotrexate monotherapy. Based on a two-sided chi-square test with 90% power, 100 subjects per arm are required at randomization.

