6.5 Study Endpoints

Patient Global Assessment of Joint Pain (PtGAJP)

An assessment of the severity of the subject's joint pain (0=no pain at all, 100=worst pain imaginable) completed by the patient using a visual analog scale (VAS) in mm.

Patient Global Assessment of Disease Activity (PtGA)

A global assessment of the subject's arthritis (0=no arthritis activity at all, 100=worst arthritis activity imaginable) completed by the patient using a visual analog scale (VAS).

Physician Global Assessment of Disease Activity (PhGA)

A global assessment of the subject's arthritis (0=no activity at all, 100=worst activity imaginable) completed by the physician using a visual analog scale (VAS).

Swollen Joint Count

A score that assesses the presence or absence of swelling in 66 joints. There are also a 28-joint Swollen Joint Count and a 28-joint Plus Feet and Ankles Swollen Joint Count. Details of the scoring algorithm are described in [Appendix A](#).

Tender Joint Count

A score that assesses the presence or absence of tenderness in 68 joints. There are also a 28-joint Tender Joint Count and a 28-joint Plus Feet and Ankles Tender Joint Count. Details of the scoring algorithm are described in [Appendix A](#).

Simplified Disease Activity Index (SDAI)

A composite score that is based on the number of tender and swollen joints using a 28-joint count, PhGA (0-10 visual analog scale), PtGA (0-10 visual analog scale), and CRP in mg/dL. A higher score represents worse disease.

Details of the scoring algorithm are described in [Appendix A](#).

SDAI Remission at Analysis Visit k

For Analysis Visits other than Week 48, SDAI Remission at a given Visit will be derived using the same approach as in [Section 6.2](#), replacing Week 48 with the Analysis Visit Week k , and replacing “subject did not fulfill the definition of disease-worsening during the study” with “subject did not *previously* fulfill the definition of disease-worsening”.

Specifically,

- SDAI_remission_maintenance (≤ 3.3) at Week $k = 1$,
if SDAI ≤ 3.3 at Week k AND subject did not previously fulfill the definition of disease-worsening;
- SDAI_remission_maintenance (≤ 3.3) at Week $k = \text{missing}$,
if subject has no Week k SDAI value AND subject did not previously fulfill the definition of disease-worsening;
- SDAI_remission_maintenance (≤ 3.3) at Week $k = 0$,
otherwise.

Observed SDAI Remission at Analysis Visit k

- Observed_SDAI_Remission at Analysis Visit $k = 1$,

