11.5.2 Secondary Efficacy Endpoint(s)

For secondary endpoints, unless otherwise noted, the Chi-squared test will be used for categorical endpoints, the t-test for continuous endpoints, and Log-rank test for time-to-event endpoints. In comparison of means, the Satterthwaite t-test may be used when variances between the two groups are different. These tests will evaluate etanercept monotherapy vs methotrexate monotherapy and etanercept and methotrexate combination therapy vs methotrexate monotherapy.

Proportion of subjects achieving SDAI remission at week 48 for the etanercept plus methotrexate treatment arm will be compared to that of the methotrexate monotherapy arm using the chi-squared test and will be presented with nominal p-values only (eg, no adjustment for multiplicity will be done). To parallel the the primary analysis of the primary estimand, the proportion of subjects in the etanercept plus methotrexate treatment arm and the methotrexate monotherapy arm achieving SDAI remission at week 48 will be evaluated using non-responder imputation, as observed data, and multiple imputation.

The proportion of subjects achieving SDAI remission (≤ 3.3), SDAI continuous score, and SDAI change from baseline at all visits will be summarized by treatment group using the PAS. Subjects with missing SDAI value at week 48 and subjects who disease-worsened are considered non-responders.

DAS28-ESR, DAS28-CRP, and CDAI, and their changes from baseline will also be summarized by visit for each treatment group using the PAS. Missing data will not be imputed for these continuous endpoints. T-tests will compare means between etanercept vs methotrexate and etanercept + methotrexate vs methotrexate.

Proportion of subjects achieving Boolean remission will be tabulated by visit for each treatment group using the PAS. Boolean remission using 28-joint-count, 28-joint-count + feet and ankles, and 66/68 joint count will be assessed.

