SDAI remission (≤ 3.3) at week 48	
Count (percentage) of subjects achieving SDAI remission as defined by SDAI_remission_maintenance detailed in Section 6.2 at Week 48 for the PAS.
 
A chi-squared test comparing etanercept plus methotrexate combination arm and methotrexate monotherapy using the PAS.
 
Subjects who have a missing SDAI_remission value will be considered as non-responders. Nominal p-values will be provided.
	
Observed_SDAI_remission using as observed approach as detailed in Section 6.5 (missing data will be excluded).
 
Multiple imputation method: impute SDAI values when missing and after rescue for randomized subjects. The composite SDAI values will be imputed rather than its components.

SDAI score and change from baseline at all measured timepoints	
Summary statistics for SDAI score and change from baseline at each Analysis Visit for the PAS.
 
T-test comparing etanercept monotherapy vs methotrexate monotherapy
 
T-test comparing etanercept and methotrexate combination therapy vs methotrexate monotherapy
	
DAS28-ESR and change from baseline at all measured timepoints	
Similar analysis as for SDAI score and change from baseline at all measured timepoints
	

Table 1. Primary and Secondary Endpoints Summary Table

Endpoint	Primary Analysis Method	Sensitivity/Exploratory Analysis
Secondary Endpoints (Continued)		
DAS28-CRP and change from baseline at all measured timepoints	Similar analysis as for SDAI score and change from baseline at all measured timepoints	
CDAI and change from baseline at all measured timepoints	Similar analysis as for SDAI score and change from baseline at all measured timepoints	
SDAI remission (≤ 3.3) at all measured timepoints	Count (percentage) of subjects achieving SDAI remission as defined by SDAI_remission_maintenance detailed in Section 6.5 for the PAS. Chi-squared test comparing etanercept monotherapy vs methotrexate monotherapy Chi-squared test comparing etanercept and methotrexate combination therapy vs methotrexate monotherapy	
Boolean remission at all measured timepoints	Observed count (percentage) of subjects achieving Boolean remission at each Analysis Visit for the PAS. Boolean remission using 28-joint-count, 28-joint-count + feet and ankles, and 66/68 joint count will be assessed. Chi-squared test comparing etanercept monotherapy vs methotrexate monotherapy Chi-squared test comparing etanercept and methotrexate combination therapy vs methotrexate monotherapy	

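### Boolean remission and the SDAI, DAS28 and CDAI scores are compared between arms with post-rescue values included, which dilutes the monotherapy contrast and is not labelled as a treatment-policy comparison

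*SAP*

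**What the plan says.** **Rescue.** Under Protocol 3.1.1, 3.1.2 and 7.2.7, a randomized subject who meets disease-worsening starts etanercept plus methotrexate, continues it for the remaining visits and completes the scheduled assessments. Combination-arm subjects stay on their assigned treatment.

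**Endpoints with a worsening rule.** SAP 6.2 scores SDAI remission at Week 48 as achieved only without disease-worsening during the study. SAP 6.5 carries this to other visits with the condition "subject did not *previously* fulfill the definition of disease-worsening". A separate Observed SDAI Remission, without that condition, is exploratory (SAP 4.1.4 and 11.5.3).

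**Endpoints without one.** The Boolean definitions in SAP 6.5 mention neither worsening nor rescue, and Table 1 gives the analysis as "Observed count (percentage) of subjects achieving Boolean remission at each Analysis Visit for the PAS", with chi-squared tests between arms. SDAI, DAS28-ESR, DAS28-CRP and CDAI scores and changes are t-tested at each visit in the same set. For DAS28 and CDAI, SAP 11.5.2 adds "Missing data will not be imputed for these continuous endpoints". Protocol 10.5.1 says "Secondary efficacy endpoints will be summarized using observed cases only". The sensitivity column of Table 1 is blank for all these rows.

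**Objective.** SAP 2.2 asks for etanercept monotherapy against methotrexate monotherapy, and the combination against methotrexate monotherapy, on disease activity and remission. SAP 4.1.1 states an estimand for the primary endpoint only.

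**The concern.** A subject randomized to methotrexate who worsens, is rescued and regains remission counts at later visits as a Boolean remitter with low scores in the methotrexate arm, while actually taking the combination. The arm that fails more often receives more combination treatment, so its later values improve more. The tests that carry the disease-activity objective are therefore diluted toward no difference, increasingly so as the rescued share grows from Week 24 to Week 48.

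The combination-versus-methotrexate tests are affected on the methotrexate side only, because rescued combination subjects continue the same treatment.

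Two secondary remission endpoints would also treat the same recaptured subject in opposite ways at Week 48: failure for SDAI remission, success for Boolean remission. The SAP gives no reason for the difference, and its Section 12 on changes from the protocol does not mention it.

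**Working it through.** **The plan's own figure.** SAP 3.2 assumes 50% (methotrexate) and 72% (etanercept) and sizes the trial for "SDAI remission at week 48 at a significance level of 0.05". It then says: "Based on a two-sided chi-square test with 90% power, 100 subjects per arm are required at randomization". With pooled rate 0.61:

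- n = [1.960 × √(2 × 0.61 × 0.39) + 1.282 × √(0.50 × 0.50 + 0.72 × 0.28)]² / 0.22² = 102 after rounding up.
- Power at 100 per arm is 89.7%.

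The stated size reproduces to within rounding and is not in dispute.

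**Inputs for the illustration.** The documents give no Boolean rate, so p = 0.50 and 0.72 serve as a stand-in. Let f be the share of non-maintainers who are rescued before Week 48, and r the share of those in remission at Week 48. Neither is in the documents. The nearest statement, in Protocol 2.4, is that in an earlier withdrawal study "most patients whose disease activity worsens after drug withdrawal are able to return to low disease activity", which is not a remission rate.

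**Formula.** Observed rate = p + (1 − p) × f × r. The arm difference is then 0.22 × (1 − f × r), which is below 0.22 for any f and r above zero.

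| f | r | Methotrexate | Etanercept | Difference (points) | Power, 100 per arm |
|---|---|---|---|---|---|
| worsening counted as failure | – | 50.0% | 72.0% | 22.0 | 90% |
| 0.6 | 0.25 | 57.5% | 76.2% | 18.7 | 81% |
| 0.8 | 0.50 | 70.0% | 83.2% | 13.2 | 60% |
| 1.0 | 0.50 | 75.0% | 86.0% | 11.0 | 50% |

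For example, at f = 0.8 and r = 0.5: 0.50 + 0.50 × 0.40 = 0.70 and 0.72 + 0.28 × 0.40 = 0.832.

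The formula keeps unrescued non-maintainers in the denominator as failures. Some would be dropouts, whom an observed count excludes. If all of them left the denominator, the differences at the second and third rows would be 13.9 points (71.9% vs 85.8%) and 10.4 points (77.8% vs 88.1%). Part of that further shrinkage comes from excluding dropouts, not from rescue.

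**Scores.** The arm difference in means is 0.22 × (mean in non-maintainers − mean in maintainers). The documents give no such means, so two assumed sets show the spread:

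- Maintainers 2, worsened and unrescued 12: 0.22 × 10 = 2.2. If all are rescued and average 5: 0.22 × 3 = 0.66.
- Maintainers 1.5, worsened and unrescued 4 (worsening can be met just above 3.3): 0.22 × 2.5 = 0.55. If 80% are rescued, of whom 70% reach 2 and 30% stay at 4, the rescued mean is 2.6, the non-maintainer mean is 0.8 × 2.6 + 0.2 × 4 = 2.88, and the difference is 0.22 × 1.38 = 0.30.

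The direction is the same in both; the size depends on the assumptions.

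**The case against.** The strongest reply is that the strategy was chosen. Protocol 10.1.2.1 and SAP 7.1 analyse efficacy endpoints by randomized arm whatever treatment was received, and the protocol prespecifies observed cases for secondary endpoints. Together these give a recognised treatment-policy comparison. This stands. What is missing is the label, and an analysis closer to the stated objective.

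Second, much of the monotherapy question is answered elsewhere. Binary SDAI remission counts prior worsening as failure, disease-worsening and time to worsening are analysed in all randomized subjects, and the course after rescue is summarized separately. This also stands, and it limits what is at stake.

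Third, a reader might infer that Boolean and SDAI remission can disagree at Week 48 only because of rescue. The documents do not support that. Boolean remission omits the physician global and caps each component, while SDAI is a sum. A missing Week 48 value is non-response for SDAI remission but drops out of an observed Boolean count. The exploratory Observed SDAI Remission gives a comparator with the same approach to rescue.

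Fourth, a reader might infer that every worsened subject becomes a rescued remitter. SAP 12 expects some who worsen without receiving rescue, and a rescued subject counts as a remitter only if remission is regained.

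One counter-argument fails. SAP 11.5.2 says that subjects who disease-worsened are non-responders, but this can apply only to a binary endpoint, not to a score.

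**Conclusion.** The concern holds in a limited form. The Boolean remission and score tests are valid as comparisons of randomized starting strategies including combination rescue. They are not the monotherapy contrast in the secondary objective, they lean toward no difference at later visits, and they have no sensitivity analysis. It would go too far to call them invalid or to say that the objective is left unanswered.

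In the illustration, the 22-point difference falls to 18.7 points under mild assumptions and to 13.2 points under stronger ones. This rests on using SDAI planning rates for Boolean remission and on assumed rescue and recapture shares. The power figures only express the dilution: these tests are nominal, carry no multiplicity adjustment and were not the basis of the sample size. Binary SDAI remission, disease-worsening, time to worsening and the primary conclusion are unaffected.

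**What to change.** **(a) Boolean remission (SAP 6.5 and Table 1).** For all three joint sets, define the secondary endpoint at each visit with the rule already used for SDAI remission: 0 once disease-worsening has previously been met. Keep the observed Boolean count as a supportive analysis, parallel to Observed SDAI Remission. State also how the worsening visit itself is scored. SDAI is above 3.3 there, but a subject could still meet the Boolean criteria, because four components at 1 each already sum to 4.

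**(b) Scores (SAP 11.5.2 and Table 1).** Keep the as-observed tests of SDAI, DAS28-ESR, DAS28-CRP and CDAI, labelled as treatment policy including combination rescue. Add a sensitivity analysis that sets post-rescue values to missing and multiply imputes them, as SAP 11.5.1.2 already does for SDAI. Do not carry the last pre-rescue value forward as the main comparison. That value was selected because it crossed a worsening threshold, so carrying it forward treats a flare as permanent, ignores imputation uncertainty and can exaggerate the difference.

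**Cost.** SAP wording and a little more programming. The disease-worsening and rescue dates are already defined in SAP 6.1, so no new data are needed. The imputation rests on a missing-at-random assumption, which is one reason to keep the as-observed tests alongside it.

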7.3 Disease-Worsening Analysis Set

The Disease-Worsening Analysis Set includes randomized subjects who meet the definition of Disease-Worsening at any point after randomization.

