11.1 General Considerations

The primary analysis will be performed after all subjects have completed the Week 48/ET assessment and the 30-day safety follow-up period and all data have been finalized.

Subject disposition, demographics, and baseline disease characteristics will be summarized descriptively by randomized treatment group.

For categorical endpoints, descriptive statistics will report frequency and percentage. For continuous endpoints, descriptive statistics will include the number of observations, mean, standard error or standard deviation, median, minimum, and maximum.

The statistical test for the primary efficacy endpoint will have a significance level of 0.05. Non-responder imputation will be employed for the missing values of the primary endpoint.

For continuous secondary endpoints, t-tests will compare 1) etanercept monotherapy vs methotrexate monotherapy, and 2) etanercept and methotrexate combination therapy vs methotrexate monotherapy. No multiplicity adjustments will be made.

For binary secondary endpoints, Chi-squared tests with continuity correction will compare 1) etanercept monotherapy vs methotrexate monotherapy, and 2) etanercept and methotrexate combination therapy vs methotrexate monotherapy. No multiplicity adjustments will be made.

For time-to-event secondary endpoints, the number of subjects achieving the event and the number of subjects censored as defined in [Section 6.4](#) will be provided.

Kaplan-Meier (KM) curves, estimates, and 95% CIs will be provided by treatment group. A two-sided log-rank test incorporating treatment group will evaluate 1) etanercept monotherapy vs methotrexate monotherapy, and 2) etanercept and methotrexate combination therapy vs methotrexate monotherapy. Median time-to-event will be provided for each of the treatment arms.

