Proportion of subjects with Disease-Worsening and time-to-disease-worsening will be evaluated by treatment group for the PAS. Time-to-disease-worsening will be evaluated using Kaplan-Meier (KM) curves, estimates, and 95% CIs by treatment group. For subjects with more than one DW Date, the first DW date will be used. Subjects who do not experience disease-worsening will be censored at last SDAI assessment date. In addition, a two-sided log-rank test will evaluate the etanercept monotherapy vs methotrexate monotherapy arms, and the etanercept plus methotrexate combination vs methotrexate monotherapy arms.

Time-to-recapture observed SDAI remission from Rescue Date will be evaluated for the Rescue Analysis Set using Kaplan-Meier (KM) curves, estimates, and 95% confidence intervals by treatment group; subjects who do not recapture SDAI remission will be censored at their last SDAI assessment date. This analysis will be repeated for Time-to-recapture SDAI remission from Disease-Worsening Date for the Disease-Worsening Analysis Set. For subjects with more than one recapture of observed SDAI remission, the first recapture date will be used. Additionally, the proportion of subjects who recapture observed SDAI remission at week 48 will be summarized for both the Rescue Analysis Set and the Disease-Worsening Analysis Set.

Table 1. Primary and Secondary Endpoints Summary Table

Endpoint	Primary Analysis Method	Sensitivity/Exploratory Analysis
Primary Endpoint		
SDAI remission (≤ 3.3) at week 48 as defined by SDAI_remission_maintenance detailed in Section 6.2	
Count (percentage) of subjects achieving SDAI remission as defined by SDAI_remission_maintenance detailed in Section 6.2 at Week 48 for the PAS.
 
A chi-squared test comparing etanercept monotherapy and methotrexate monotherapy using the PAS.
 
Subjects who have a missing SDAI_remission value will be considered as non-responders.
	
Observed_SDAI_remission using as observed approach as detailed in Section 6.5 (missing data will be excluded).
 
Multiple imputation method: impute SDAI values when missing and after rescue for randomized subjects. The composite SDAI values will be imputed rather than its components.

Secondary Endpoints		

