Disease-Worsening defined as an SDAI > 3.3 and ≤ 11 during two consecutive visits at least 2 weeks apart or SDAI > 3.3 and ≤ 11 on three or more separate visits or SDAI > 11 after randomization	Observed count (percentage) of subjects fulfilling Disease-Worsening criteria at each Analysis Visit for the PAS.	

Table 1. Primary and Secondary Endpoints Summary Table

Endpoint	Primary Analysis Method	Sensitivity/Exploratory Analysis
Secondary Endpoints (Continued)		
Time to Disease-Worsening as an SDAI > 3.3 and ≤ 11 during two consecutive visits at least 2 weeks apart or SDAI > 3.3 and ≤ 11 on three or more separate visits or SDAI > 11 after randomization	Kaplan-Meier curves, estimates, and 95% CIs assessing Time to Disease-Worsening by treatment group for the PAS. Subjects with more than one DW Date will be analyzed using the first DW Date. Subjects who do not experience disease-worsening will be censored at last SDAI assessment date. Log-rank test comparing etanercept monotherapy versus methotrexate monotherapy. Log-rank test comparing etanercept and methotrexate combination therapy versus methotrexate monotherapy.	
Time to recapture observed SDAI remission after starting rescue treatment	Kaplan-Meier curves assessing Time to recapture observed SDAI remission from Rescue Date for the Rescue Analysis Set. Subjects with more than one recapture of SDAI remission will be analyzed using their first recapture date. Subjects who do not recapture SDAI remission are censored at their last SDAI assessment date. Log-rank test comparing etanercept monotherapy versus methotrexate monotherapy. Log-rank test comparing etanercept and methotrexate combination therapy versus methotrexate monotherapy.	Similar analysis as the Primary Analysis Method but using the Disease-Worsening Analysis Set, looking at time to recapture SDAI remission from DW Date.
Observed SDAI remission at Week 48	Observed count (percentage) of subjects achieving SDAI remission as defined by Observed_SDAI_remission as detailed in Section 6.5 at Week 48 for the Rescue Analysis Set.	Similar analysis as the Primary Analysis Method but using the Disease-Worsening Analysis Set.

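### Between-arm p-values for remission recapture compare subsets selected by worsening after randomisation, so a difference cannot be separated from selection

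*SAP*

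**What the plan says.** SAP 7.3 defines the first set by an event after randomisation: "The Disease-Worsening Analysis Set includes randomized subjects who meet the definition of Disease-Worsening at any point after randomization". SAP 7.4 adds the requirement that the subject received at least one dose of each active rescue drug.

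The text of SAP 11.5.2 states "Time-to-recapture observed SDAI remission from Rescue Date will be evaluated for the Rescue Analysis Set using Kaplan-Meier" curves, estimates and confidence intervals, and names no test in that paragraph. Table 1 does name them. Its row on time to recapture after rescue lists a "Log-rank test comparing etanercept monotherapy versus methotrexate monotherapy" and a second log-rank test of combination against methotrexate. The sensitivity column repeats the analysis in the Disease-Worsening set, timed from worsening. SAP 11.1 and the opening of 11.5.2 also apply the log-rank test to time-to-event secondary endpoints generally.

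Table 2 (SAP 11.5.3) adds chi-squared tests, t-tests and log-rank tests in these two sets, for example for remission at visits after rescue, SDAI score at worsening and time to DAS28-ESR remission.

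Protocol 3.1.1 and SAP 6.3 say that combination-arm subjects who worsen stay on their assigned treatments; SAP 6.3 still counts them as being on rescue. Neither document describes the comparisons within these sets as non-randomised or adjusts them for severity.

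**The concern.** A log-rank p-value is read as evidence on whether two arms differ. That reading is protected by randomisation when all randomised subjects are compared. Here entry to the analysis requires having worsened on the assigned arm, and the trial is built on the hypothesis that fewer will do so on etanercept than on methotrexate. Those who worsen on the arm that holds remission better may be a more severe selection. If severity also slows recapture, the two groups differ before rescue starts, and the test can reject although rescue works equally well in both.

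At stake is the reading of a stated secondary objective (Protocol 1.2, SAP 2.2), which frames recapture after rescue as a comparison of efficacy between arms. A small p-value could be reported as faster recapture after one monotherapy than after the other, when the analysis cannot show that.

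**Working it through.** **1. The plan's own figure.** SAP 3.2 assumes remission of 50% on methotrexate and about 72% on etanercept and states: "Based on a two-sided chi-square test with 90% power, 100 subjects per arm are required at randomization". With p̄ = 0.61 and difference 0.22:

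n = [1.960·√(2·0.61·0.39) + 1.282·√(0.72·0.28 + 0.50·0.50)]² / 0.22² = (1.352 + 0.861)² / 0.0484 ≈ 101.2, so 102 per arm without continuity correction. Power at 100 per arm is 89.7%. The stated 100 reproduces to within rounding. No size, power or error rate is stated for the tests in the selected sets.

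**2. How many can enter the sets.** Under SAP 6.2 anyone who worsens is a primary non-responder, so non-response bounds entry from above:

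- etanercept: 100 × (1 − 0.72) = 28
- methotrexate: 100 × (1 − 0.50) = 50
- combination, on the prior-study rates in SAP 3.2 (86.1% and 78.3%): 50 × 0.139 = 7 to 50 × 0.217 = 11

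These are ceilings. Missing Week 48 data also count as non-response (SAP 11.5.1.1). So does a single Week 48 SDAI above 3.3 and up to 11 that never meets the worsening definition. The Rescue set also requires both rescue drugs to have been taken.

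**3. A two-class illustration (assumed).** Let 20% of each arm be refractory, with a further 30% (methotrexate) or 8% (etanercept) worsening only because of withdrawal. Let the chance of recapture at each visit be 30% if refractory and 70% otherwise, the same in both arms. First-visit recapture is then:

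- methotrexate: (20·0.3 + 30·0.7)/50 = 27/50 = 54%
- etanercept: (20·0.3 + 8·0.7)/28 = 11.6/28 = 41%

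Rescue works equally for each type of patient; only the mix differs. Simulated trials of 100 per arm gave log-rank rejection of 21-23%. Milder inputs gave less:

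- recapture 40% v 60%: 9-11%
- 10% refractory, same totals: about 10-11%
- 10% refractory with recapture 50% v 70%: 6%
- three-quarters as many subjects worsening: 17%
- no severity link: 5.1%

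**4. A graded model (assumed).** Severity U is standard normal. A subject worsens if ρU + √(1−ρ²)·ε exceeds the cut-off that gives the arm's worsening rate (28% etanercept, 50% methotrexate, 18% combination). The weekly recapture hazard is 0.06·exp(−βU) in every arm. Rescue starts at week 12, 24 or 36 with equal chance, recapture is seen at 12-weekly visits, and follow-up ends at week 48. There were 4,000 runs per row.

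| ρ, β | Mean recapture, etanercept / methotrexate | Rejection, etanercept v methotrexate | Rejection, combination v methotrexate |
|---|---|---|---|
| 0, 0 | 72.0% / 72.2% | 4.8% | 4.9% |
| 0, 1 | 68.1% / 67.7% | 5.1% | 5.3% |
| 0.9, 0 | 72.2% / 72.1% | 5.1% | 5.3% |
| 0.5, 0.5 | 61.9% / 65.1% | 6.3% | 6.0% |
| 0.5, 1 | 53.4% / 58.4% | 7.3% | 6.8% |
| 0.7, 1 | 46.7% / 54.6% | 10.7% | 8.9% |
| 0.7, 1.5 | 38.5% / 48.3% | 12.8% | 10.1% |
| 0.9, 1 | 39.6% / 50.0% | 14.4% | 11.9% |
| 0.9, 1.5 | 29.2% / 42.4% | 20.1% | 16.6% |
| 0.9, 2 | 22.4% / 36.9% | 26.4% | 17.8% |

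The test holds 5% only when severity does not drive both worsening and recapture. If methotrexate worsened at the prior-study rate (1 − 0.381 = 61.9%), rejection would be 7.6% at (0.5, 0.5), 17.4% at (0.7, 1) and 53.7% at (0.9, 2). That is not the plan's assumption.

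**5. Combination against methotrexate.** No simulation is needed. At rescue a methotrexate subject has etanercept added back, while a combination subject changes nothing. The test sets a change of treatment against no change, in at most about 7-11 against 50 subjects.

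**The case against.** Several points on the other side stand.

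- **The error rate is not known.** A reader might take one simulated scenario, say 23%, as the test's actual error. Every driver behind it is assumed, and plausible milder inputs give 6-11%. Only the range can be reported.
- **50% and 28% are not entry rates.** A reader might infer that these shares of the arms enter the sets. They are complements of assumed Week 48 remission, and so upper bounds.
- **A difference need not be selection alone.** Etanercept-arm subjects regain methotrexate and methotrexate-arm subjects regain etanercept, so response to re-treatment may truly differ. The documents support only that the test cannot tell the two apart. The direction of any bias also rests on assumptions.
- **Not every log-rank test in Table 1 is affected.** The quoted sentence also appears in the row on time to disease worsening. That test uses all randomised subjects and is sound.
- **The Week 48 recapture row of Table 1 lists counts only.** A chi-squared test reaches it only through the general rule in SAP 11.5.2.
- **These are secondary and exploratory analyses.** No power is attached to them. The primary endpoint and time to worsening address withdrawal in all randomised subjects, so harm to decisions about which drug to withdraw is speculative.

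One could instead keep the p-values and label them nominal and non-randomised. That would be an improvement, but it would leave a number with no clear interpretation, and in the combination comparison one that does not concern rescue. Protocol 10.5.3 does not require it: it asks only that time to recapture be analysed and names no test between arms.

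**Conclusion.** The point holds for the recapture row of Table 1, its repeat in the Disease-Worsening set, and the between-arm tests of Table 2 in those two sets. Following the plan gives p-values that cannot be read as an effect on recapture after rescue.

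For etanercept against methotrexate, with equally effective rescue and the plan's planning rates, rejection is about 5% without a severity link, 6-11% with a mild to moderate one and roughly 20-26% with a strong one. This rests on assumed severity, recapture and rescue-timing inputs, and on set sizes at their upper bounds. For combination against methotrexate the objection does not depend on any of these, because one side has no rescue change to assess.

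The documents do not support going further, to a claim that an observed difference would be wholly selection or that the trial's main conclusions are at risk. The primary analysis and the time-to-worsening test are untouched. This should be corrected, but it is not critical.

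**What to change.** In the affected rows of Tables 1 and 2, and as a stated exception to the general testing rules in SAP 11.1, 11.5.2 and 11.5.3, remove the between-arm p-values in the Rescue and Disease-Worsening sets. Keep Kaplan-Meier curves, rates and confidence intervals by arm. The SAP already takes this course in the Disease-Worsening set for reason for worsening, where it rules out testing.

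The label matters as much as the removal, since curves by arm invite the same misreading. Suggested wording: *Results in these sets are descriptive summaries of subsets formed after randomisation and are not randomised comparisons. Combination-arm subjects had no change of assigned treatment at rescue.*

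For a comparison that starts from the randomised arms, point to observed SDAI remission at Week 48 in the Primary Analysis Set, already planned in Tables 1 and 2. State its limits: it describes Week 48 status regardless of rescue, leaves out subjects with no Week 48 value, and does not measure time to recapture.

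The cost is a change of SAP wording, with no new data. The downside is that the recapture part of a secondary objective is answered descriptively and not by a test.
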